8.5. Analysis of Secondary Efficacy Endpoints

The assessments associated with the secondary efficacy endpoints for this study are conducted at multiple time points during the randomized withdrawal period: Visit 6 (Day 113, baseline), Visit 7 (Day 127), Visit 8 (Day 141), and Visit 9 (Day 155). Hence, a mixed effects model for repeated measures (MMRM) will be fitted to analyze the secondary efficacy endpoints that have data available:

- OHSA#1
- OHSA composite score
- OHDAS composite score
- PGI-S
- Percentage of time spent in standing position (including walking) while wearing the device
- Average number of steps taken per hour while wearing the device

The change from baseline (or equivalently the postbaseline value) will be used as the dependent variable in the model. The model will include terms for treatment, disease type (MSA, PD, PAF), visit, and treatment by visit interactions, and the baseline value of the endpoint as a continuous covariate. Within-subject correlation will be modelled using an unstructured variance-covariance matrix. The Kenward and Roger method for approximating the denominator degrees of freedom will be used. Missing endpoint values will be assumed to be missing at random (MAR). If the

model does not converge, the data will be reanalyzed fitting a compound symmetric covariance structure (type=CS) and a compound symmetric with heterogenous variance covariance structure (type=CSH) and the structure with a lower AIC value will be selected.

LS mean change for each treatment group and the difference in the LS mean change between treatment groups with respect to the secondary endpoint analyzed will be estimated by fitting the MMRM model. Standard errors, 95% confidence intervals, and p-values will be provided.

Subgroup Analyses

To assess consistency of treatment differences across subgroups, the analysis of the secondary endpoints will be repeated for each of the subgroups specified in Section 6.2.8.

8.6. Multiple Testing Plan

If the primary endpoint is met, i.e., the TD-9855 vs. placebo odds of treatment failure at Week 6 post randomization (V9, D155) point estimate is < 1 and the 2-sided p-value is < 0.05 , secondary efficacy endpoints will be tested in the sequence shown below until the first failure to reject a null hypothesis occurs.

1. Change from baseline in OHSA#1 at Week 6 post randomization (V9, D155)
2. Change from baseline in OHSA composite score at Week 6 post randomization (V9, D155)
3. Change from baseline in OHDAS composite score at Week 6 post randomization (V9, D155)
4. Change from baseline in PGI-S at Week 6 post randomization (V9, D155)
5. Change from baseline in percentage of time spent in standing position (including walking) as measured by a wearable device at Week 6 post randomization (V9, D155)
6. Change from baseline in average number of steps taken as measured by a wearable device at Week 6 post randomization (V9, D155)

This controls the familywise type 1 error rate at 0.05.

For all other analyses, there will be no adjustments for multiplicity.

8.7. [REDACTED]

[REDACTED]

[REDACTED]

[REDACTED]

1. [REDACTED]
[REDACTED]
2. [REDACTED]
[REDACTED]

¶ [REDACTED]
[REDACTED]

¶ [REDACTED]

[REDACTED]
[REDACTED]

[REDACTED]
[REDACTED]
[REDACTED]
[REDACTED]
[REDACTED]

¶ [REDACTED]
[REDACTED]

¶ [REDACTED]
[REDACTED]
[REDACTED]
[REDACTED]

¶ [REDACTED]

¶ [REDACTED]

¶ [REDACTED]
[REDACTED]

¶ [REDACTED]
[REDACTED]
[REDACTED]
[REDACTED]
[REDACTED]
[REDACTED]

¶ [REDACTED]
[REDACTED]

¶ [REDACTED]
[REDACTED]

¶ [REDACTED]
[REDACTED]

¶ [REDACTED]
[REDACTED]

[REDACTED]
[REDACTED]
[REDACTED]

8.7.1. Falls

Falls and near-falls are the only count-data exploratory endpoints. They will be summarized descriptively, by showing counts and percentages of subjects with at least 1 fall during each treatment period and by showing counts and percentages of subjects with at least 1 fall or near-fall during each treatment period. In addition, for falls and for falls + near-falls, the following categorical summaries with counts and percentages will be provided:

- None
- 1
- 2
- 3 or more

For the randomized withdrawal treatment period, these summaries will also be provided for the 3 disease type subgroups, and the MSA subgroup summary will adjust for a measure of motor function, UMSARS Part II score, by presenting counts and percentages both overall and by dichotomized score subgroup: ≤ 22 (the median baseline score) and ≥ 23 . The PD subgroup summary was also to be adjusted for a measure of motor function, Modified Hoehn and Yahr Stage (Table 4). This was not necessary, however, since the reported stage was 1 for almost all of the PD subjects who entered the randomized withdrawal treatment period.

Table 4. Modified Hoehn and Yahr Staging

Stage	Modified Hoehn and Yahr Scale
1	Unilateral involvement only
1.5	Unilateral and axial involvement
2	Bilateral involvement without impairment of balance
2.5	Mild bilateral disease with recovery on pull test
3	Mild to moderate bilateral disease; some postural instability; physically independent
4	Severe disability; still able to walk or stand unassisted
5	Wheelchair bound or bedridden unless aided

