6.4.6.8. Incidence of Falls – Subject Diary

Falls in subjects with symptomatic nOH are common and potentially catastrophic. They can lead to serious injuries including hip fractures or head trauma; furthermore, fear of falling can limit mobility and physical activity. Thus, incidence of subject-reported falls is being captured in a diary. Assessments will be performed as specified in the Schedule of Study Procedures (Table 1). An example of the instrument is provided in Appendix 3.

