8.5.1.2. Secondary and Other Efficacy Evaluations

Secondary efficacy endpoints involving assessment of change from baseline at multiple time points such as OHSA#1, OHSA composite score, OHDAS composite score, and percent of time spent in supine, sitting and standing position as measured by a wearable device, will be analyzed using mixed model for repeated measures (MMRM) to compare treatment differences based on the FAS. The model will include fixed effect class terms of treatment, baseline disease type (MSA, PD, PAF), week, and continuous covariate of baseline score of the respective measure, a random subject effect, with an unstructured covariance structure. If the model doesn't converge, compound symmetry or other covariance structures will be used as alternative covariance structure. Least-square means and 95% confidence intervals on the differences between TD-9855 and PBO will be calculated and presented.

Exploratory endpoints involving assessment of change from baseline at multiple time points such as standing SBP during orthostatic standing test will be analyzed using mixed model for repeated measures (MMRM) to compare treatment differences based on the FAS.

Exploratory endpoints involving assessment of change from baseline but only at Week 6 such as PDQ-8, UPDRS, UMSARS, and COMPASS-31 an analysis of covariance (ANCOVA) will be used to compare treatment differences based on the FAS. The model will include fixed effect of treatment, baseline disease type (MSA, PD, PAF) and continuous covariate of baseline score of the respective scales.

All other efficacy endpoints will be analyzed descriptively as supportive analysis.

In addition, descriptive analysis of efficacy data collected during OL phase will be carried out for all subjects and summarized by enrollment group (De Novo Group or 0169 Completers Group).

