APPENDIX 3. INCIDENCE OF FALLS

Protocol 0170 - Fall Diary

Subject ID: _____

Visit Dispensed: _____

Date Returned: _____

Instructions:

- 1) For each Time of Day, entry should be made at the end of that time period.
- 2) If you did not fall or have a near-fall, put a check mark in the No Falls or No Near-Falls box for that time of day.
- 3) If you had a fall or near-fall, record the number of Falls or Near-Falls in the appropriate box for that time of day.

Definitions:

A fall is defined as: an unexpected event in which you come to rest on the ground, floor, or lower level.

A near-fall is defined as: losing your balance but managing to stay upright, for example by holding on to something or someone.

Day of the Week/ Date	Time of Day	No Falls	No Near-Falls	Falls	Near-Falls
Day of the Week:	Morning: Awakening to 12PM			Number =	Number =
	Afternoon: 12 PM to Bedtime			Number =	Number =
Date:	Night: Bedtime to Awakening			Number =	Number =
	Morning: Awakening to 12PM			Number =	Number =
Day of the Week:	Afternoon: 12 PM to Bedtime			Number =	Number =
	Night: Bedtime to Awakening			Number =	Number =
Date:	Morning: Awakening to 12PM			Number =	Number =
	Afternoon: 12 PM to Bedtime			Number =	Number =
Day of the Week:	Night: Bedtime to Awakening			Number =	Number =
	Morning: Awakening to 12PM			Number =	Number =
Date:	Afternoon: 12 PM to Bedtime			Number =	Number =
	Night: Bedtime to Awakening			Number =	Number =
Day of the Week:	Morning: Awakening to 12PM			Number =	Number =
	Afternoon: 12 PM to Bedtime			Number =	Number =
Date:	Night: Bedtime to Awakening			Number =	Number =
	Morning: Awakening to 12PM			Number =	Number =

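### Falls and near-falls are collected as dated counts but reported only as percentages, with no allowance for time observed and no rate or between-arm estimate

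*SAP*

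**What the plan says.** Protocol Appendix 3 (falls diary) splits each dated day into morning, afternoon and night and tells the subject: "If you had a fall or near-fall, record the number of Falls or Near-Falls in the appropriate box for that time of day". Table 1 of the protocol schedules the diary from screening through Visit 9, so dated counts exist for the open-label and the randomized periods. Protocol 6.4.6.8 gives the reason for collecting them: "Falls in subjects with symptomatic nOH are common and potentially catastrophic".

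SAP 8.7.1 states: "Falls and near-falls are the only count-data exploratory endpoints". It then plans two displays per treatment period. The first is set out as "They will be summarized descriptively, by showing counts and percentages of subjects with at least 1 fall during each treatment period", and the same is done for at least one fall or near-fall. The second is introduced by "for falls and for falls + near-falls, the following categorical summaries with counts and percentages will be provided" and has the levels none, 1, 2, and 3 or more. In the randomized period the displays are repeated by disease type. For MSA, motor function is handled "by presenting counts and percentages both overall and by dichotomized score subgroup", the cut being a UMSARS Part II score of 22 or less against 23 or more. SAP 6.1 puts the arms in adjacent columns, but SAP 8.7.1 names no mean count, rate, offset, rate ratio, confidence interval or test.

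Two other SAP sections bear on this. Section 8.4.1 provides for subjects who missed the Week 6 visit because the sponsor ended the study early. Section 9.3 reports midodrine use as uses per 28 days of treatment-period duration.

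**The concern.** There are two separate weaknesses.

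- **Truncated counts.** A subject with 3 falls in six weeks and one with 40 fall in the same cell. A drug that halves falls among frequent fallers leaves both displays unchanged unless those subjects drop to 2 or fewer.
- **Time observed is ignored.** A subject followed for three weeks has had less opportunity to fall than one followed for six, yet both count equally in the denominator. If stopping or missing diary days differ between arms, the arm observed for less time looks better. For the same reason, the 16-week open-label percentages cannot be set beside the 6-week randomized ones.

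The stake is interpretive. Falls are an outcome that the protocol links to hip fracture and head trauma, and the randomized period yields no effect estimate for them. Similar percentages of fallers could be read as no effect on falls.

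**Working it through.** **Inputs from the documents.** Protocol 8.2: 154 randomized, two-sided 5%, failure 25% against 50%, 90% power. Protocol 3.1 and SAP 4.4: 1:1 allocation. Follow-up of 6 weeks.

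**The plan's own figure.** With a pooled-variance test, n per arm = [(1.960√(2 × 0.375 × 0.625) + 1.282√(0.5 × 0.5 + 0.25 × 0.75)) / 0.25]² = 76.7, so 77 per arm and 154 in total; power at 77 is 90.1%. The figure reproduces. It concerns the primary endpoint only; no figure is stated for falls.

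**Assumed, because the documents are silent.** Negative binomial counts with placebo mean m per 6 weeks, dispersion k (variance m + km²) and rate ratio 0.5, with 77 complete records per arm.

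**Rate model.** Var(log rate ratio) = [(1/m₀ + k) + (1/m₁ + k)] / 77.

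- m₀ = 3, m₁ = 1.5, k = 2: variance 5/77, SE 0.255; power = Φ(0.693/0.255 − 1.960) = Φ(0.76) = 78%.
- m₀ = 0.5, m₁ = 0.25, k = 2: variance 10/77, SE 0.360; power = Φ(1.923 − 1.960) = 49%.

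**At least one fall.** P = 1 − (1 + km)^(−1/k), then a two-proportion test.

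- m₀ = 3: 1 − 7^(−1/2) = 62% against 1 − 4^(−1/2) = 50%; power 33%.
- m₀ = 0.5: 1 − 2^(−1/2) = 29% against 1 − 1.5^(−1/2) = 18%; power 36%.

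**Four planned categories.** Wilcoxon test on counts capped at 3, 40,000 simulated trials: 51% at m₀ = 3 and 40% at m₀ = 0.5.

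| Placebo mean per 6 weeks (k = 2) | Rate model | Four categories | At least 1 |
|---|---|---|---|
| 3 | 78% | 51% | 33% |
| 0.5 | 49% | 40% | 36% |

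**Information kept**, as a share of the full-count Fisher information on the log rate, for k from 0 to 4:

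| Mean per 6 weeks | Four categories | At least 1 |
|---|---|---|
| 0.25 | 94–100% | 66–88% |
| 1 | 70–97% | 40–58% |
| 2 | 55–86% | 30–33% |
| 3 | 46–68% | 16–26% |
| 5 | 33–42% | 3–21% |

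**Time observed.** Take the same true rate for everyone: mean 2 per 6 weeks, k = 1. Over 6 weeks P(at least 1) = 1 − 1/3 = 67% and P(3 or more) = (2/3)³ = 30%. Over 3 weeks the mean is 1, giving 1 − 1/2 = 50% and (1/2)³ = 13%. At arm level the at-least-one distortion is about 16.7 points times the between-arm difference in the share stopping at 3 weeks. If that difference were 20 points, the artefact would be 0.20 × 16.7 = 3.3 points.

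**The case against.** The strongest defence is that the SAP does what the protocol prescribes. Falls are not among the endpoints listed in Protocol 3.4.2 or 3.4.4, and Protocol 8.5.1.2 says: "All other efficacy endpoints will be analyzed descriptively as supportive analysis". Falls are unpowered, lie outside the testing sequence in SAP 8.6, and SAP section 6 keeps all data in listings. This stands: there is no breach and no confirmatory claim is touched. It does not make a rate unnecessary, because listings give no comparison of arms.

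Three stronger readings are tempting, and the documents do not support them.

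- A reader might infer that most of the information is thrown away. The four-category table loses more than half only above roughly 2.5 to 4 events per subject per 6 weeks; at a mean of 1 it loses at most about 30%. Such frequent events are plausible for falls plus near-falls, but no rate is documented. Comparing the rate model with the at-least-one line alone (placebo mean 0.5 to 6, dispersion 1 to 4, rate ratio 0.5 to 0.6) gives a gap of 8 to 59 points. That leaves out a display the SAP does plan. Against a rank test on the four categories, the gap is about 5 to 39 points.
- A reader might infer that the UMSARS split leaves confounding. The arms are randomized and stratified by disease type (SAP 4.4), so within MSA they differ on motor score only by chance. A continuous covariate buys precision and adjusts for chance imbalance.
- A reader might infer that a falls test is underpowered. SAP 8.7.1 plans no test, and sponsor termination means 77 complete records per arm cannot be assumed. The power figures only rank the methods.

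**Conclusion.** The point holds as a low-cost improvement. SAP 8.7.1 specifies no rate, no exposure adjustment and no between-arm estimate for data it calls counts, while the same SAP reports midodrine use per unit time.

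The firmest part is the missing allowance for time observed, which needs no assumption about how often subjects fall. The size of any distortion does need one, and a bias between arms arises only if observed time differs by arm; the documents do not say that it does.

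The loss from truncation is an assumed range. At a rate ratio of 0.5 and dispersion 2, the rate model gains about 27 points over the four categories at a placebo mean of 3 (78 − 51) and about 9 points at a mean of 0.5 (49 − 40). These figures rest on negative binomial counts and full follow-up at the planned size. The primary and secondary conclusions are unaffected.

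**What to change.** Keep the percentage tables. For the randomized withdrawal period, add to SAP 8.7.1, for falls and for falls plus near-falls:

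- events per unit of diary time in each arm;
- a TD-9855:placebo rate ratio with 95% CI from a negative binomial regression, labelled nominal, with log(diary days observed) as offset and terms for treatment, disease type and the subject's open-label event rate before Visit 6. Fix that baseline term in advance, for example log((events + 0.5)/diary days) over the last 28 days, so that subjects with no open-label events have a defined value;
- in the MSA subgroup, baseline UMSARS Part II as a continuous covariate.

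The cost is SAP wording and one model form on data already collected. It adds nominal exploratory estimates, spends no alpha, and needs a leverage check for extreme counts. The offset corrects for unequal time at a constant rate; it does not correct for subjects who stop because they are falling more, so the text should say so.

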8.8. Scoring of Clinical Outcome Assessments

8.8.1. Orthostatic Hypotension Questionnaire (OHQ)

The OHQ has 2 parts, the Orthostatic Hypotension Symptom Assessment (OHSA) to measure the presence and severity of symptoms and the Orthostatic Hypotension Daily Activity Scale (OHDAS) to measure the impact of orthostatic symptoms on daily activities. The recall period is “over the past week.”

The OHSA has 6 questions, each rating the intensity of one characteristic symptom of NOH:

7. Dizziness, lightheadedness, feeling faint, or feeling like you might black out
8. Problems with vision (blurring, seeing spots, tunnel vision, etc.)
9. Generalized weakness
10. Fatigue
11. Trouble concentrating
12. Head/neck discomfort

The OHDAS has 4 questions that assess the impact of NOH symptoms on daily activities. The responses are scored from 0 to 10, with 0 indicating no symptoms/no interference and 10 indicating the worst possible symptoms/complete interference. Respondents may select “cannot be done for other reasons,” which will be treated as a missing response when scores are calculated.

OHSA and OHDAS composite scores are an unweighted average of the scores of their nonmissing constituent items. The OHQ overall composite score is calculated as:

$$\frac{1}{2} \times \left(\frac{\text{Sum of non-missing OHSA item scores}}{\text{Number of non-missing OHSA items}} + \frac{\text{Sum of non-missing OHDAS item scores}}{\text{Number of non-missing OHDAS items}} \right)$$

The calculated OHSA and OHDAS composite scores and OHQ overall composite score will be rounded to 1 decimal place.

The table content is completely redacted with black bars.

Table 5. Schwab and England ADL Scale


100% = Completely independent. Able to do all chores without slowness, difficulty, or impairment. Essentially normal. Unaware of any difficulty.
 
90% = Completely independent. Able to do all chores with some degree of slowness, difficulty, and impairment. Might take twice as long. Beginning to be aware of difficulty.
 
80% = Completely independent in most chores. Takes twice as long. Conscious of difficulty and slowness.
 
70% = Not completely independent. More difficulty with some chores. Three to four times as long in some. Must spend a large part of the day with chores.
 
60% = Some dependency. Can do most chores, but exceedingly slowly and with much effort. Errors; some impossible.
 
50% = More dependent. Help with half, slower, etc. Difficulty with everything.
 
40% = Very dependent. Can assist with all chores, but do few alone.
 
30% = With effort, now and then does a few chores alone or begins alone. Much help needed.
 
20% = Nothing alone. Can be a slight help with some chores. Severe invalid.
 
10% = Totally dependent, helpless. Complete invalid.
 
0% = Vegetative functions such as swallowing, bladder and bowel functions are not functioning. Bedridden.

A medical professional who specializes in Parkinson’s disease assesses each item of the UPDRS. The items in Parts 1–4 yield a possible maximum of 199 points, representing maximal disability, with a score of zero representing no disability. Scores for Parts 1–4 are calculated as the sum of the item scores, excluding items that could not be rated. The total score for Parts 1–4 is calculated as the sum of the scores for the parts.

All UPDRS parts will be completed on Day 1 for De Novo subjects, while only Parts 2 and 3 of the questionnaire will be completed for subjects rolling over from Study 0169. At later visits, only Parts 2 and 3 will be administered.

8.8.3. [REDACTED]
[REDACTED]
[REDACTED]
[REDACTED]
[REDACTED]
[REDACTED]
[REDACTED]

[REDACTED]
[REDACTED]
[REDACTED]
[REDACTED]
[REDACTED]

[REDACTED]
[REDACTED]

[REDACTED]
[REDACTED]
[REDACTED]
[REDACTED]
[REDACTED]
[REDACTED]
[REDACTED]
[REDACTED]

[REDACTED]
[REDACTED]
[REDACTED]

[REDACTED]

[REDACTED]

[REDACTED]

[REDACTED]

[REDACTED]

[REDACTED]	[REDACTED]	[REDACTED]	[REDACTED]
[REDACTED]	[REDACTED]	[REDACTED]	[REDACTED]
[REDACTED]	[REDACTED]	[REDACTED]	[REDACTED]
[REDACTED]	[REDACTED]	[REDACTED]	[REDACTED]
[REDACTED]	[REDACTED]	[REDACTED]	[REDACTED]
[REDACTED]	[REDACTED]	[REDACTED]	[REDACTED]
[REDACTED]	[REDACTED]	[REDACTED]	[REDACTED]

[REDACTED]	[REDACTED]	[REDACTED]	[REDACTED]
	[REDACTED]	[REDACTED]	[REDACTED]
[REDACTED]	[REDACTED]	[REDACTED]	[REDACTED]
	[REDACTED]	[REDACTED]	[REDACTED]
	[REDACTED]	[REDACTED]	[REDACTED]
	[REDACTED]	[REDACTED]	[REDACTED]
[REDACTED]	[REDACTED]	[REDACTED]	[REDACTED]
	[REDACTED]	[REDACTED]	[REDACTED]
	[REDACTED]	[REDACTED]	[REDACTED]
	[REDACTED]	[REDACTED]	[REDACTED]
	[REDACTED]	[REDACTED]	[REDACTED]
	[REDACTED]	[REDACTED]	[REDACTED]
	[REDACTED]	[REDACTED]	[REDACTED]
	[REDACTED]	[REDACTED]	[REDACTED]
	[REDACTED]	[REDACTED]	[REDACTED]
	[REDACTED]	[REDACTED]	[REDACTED]
[REDACTED]	[REDACTED]	[REDACTED]	[REDACTED]
	[REDACTED]	[REDACTED]	[REDACTED]
	[REDACTED]	[REDACTED]	[REDACTED]
[REDACTED]	[REDACTED]	[REDACTED]	[REDACTED]
	[REDACTED]	[REDACTED]	[REDACTED]
	[REDACTED]	[REDACTED]	[REDACTED]
	[REDACTED]	[REDACTED]	[REDACTED]
	[REDACTED]	[REDACTED]	[REDACTED]

Table 7: Weight [REDACTED]

[REDACTED]	[REDACTED]	[REDACTED]	[REDACTED]	[REDACTED]
[REDACTED]	[REDACTED]	[REDACTED]	[REDACTED]	[REDACTED]
[REDACTED]	[REDACTED]	[REDACTED]	[REDACTED]	[REDACTED]
[REDACTED]	[REDACTED]	[REDACTED]	[REDACTED]	[REDACTED]
[REDACTED]	[REDACTED]	[REDACTED]	[REDACTED]	[REDACTED]
[REDACTED]	[REDACTED]	[REDACTED]	[REDACTED]	[REDACTED]
[REDACTED]	[REDACTED]	[REDACTED]	[REDACTED]	[REDACTED]
[REDACTED]	[REDACTED]	[REDACTED]	[REDACTED]	[REDACTED]
[REDACTED]	[REDACTED]	[REDACTED]	[REDACTED]	[REDACTED]

[REDACTED]

[REDACTED]

[REDACTED]

[REDACTED]

[REDACTED]

[REDACTED]

- [REDACTED]
- [REDACTED]
- [REDACTED]
- [REDACTED]
- [REDACTED]
- [REDACTED]
- [REDACTED]
- [REDACTED]
- [REDACTED]
- [REDACTED]

[REDACTED]

[REDACTED]

[REDACTED]

[REDACTED]

[REDACTED]

[REDACTED]

[REDACTED]

[REDACTED]

[REDACTED]

[REDACTED]

[REDACTED]

[REDACTED]

[REDACTED]

[REDACTED]

[REDACTED]

[REDACTED]

[REDACTED]

[REDACTED]

[REDACTED]

[REDACTED]

[REDACTED]

[REDACTED]

[REDACTED] [REDACTED]

[REDACTED]	[REDACTED]
[REDACTED]	[REDACTED]
[REDACTED]	[REDACTED]
[REDACTED]	[REDACTED]
[REDACTED]	[REDACTED]
[REDACTED]	[REDACTED]
[REDACTED]	[REDACTED]
[REDACTED]	[REDACTED]
[REDACTED]	[REDACTED]
[REDACTED]	[REDACTED]
[REDACTED]	[REDACTED]
[REDACTED]	[REDACTED]
[REDACTED]	[REDACTED]
[REDACTED]	[REDACTED]
[REDACTED]	[REDACTED]
[REDACTED]	[REDACTED]
[REDACTED]	[REDACTED]
[REDACTED]	[REDACTED]
[REDACTED]	[REDACTED]
[REDACTED]	[REDACTED]
[REDACTED]	[REDACTED]
[REDACTED]	[REDACTED]
[REDACTED]	[REDACTED]
[REDACTED]	[REDACTED]
[REDACTED]	[REDACTED]
[REDACTED]	[REDACTED]
[REDACTED]	[REDACTED]
[REDACTED]	[REDACTED]

